ESP2 hypothesises that trial managers who use the guided prediction form will be able to predict whether a site will be a 'good' site and recruit to target. If confirmed, such knowledge would enable energy and resources to be targeted more effectively using a simple form together with trial managers' experience.

OUTCOME MEASURES

Primary outcome measure

- The primary outcome is the proportion of correct predictions made by trial managers of sites that fail to recruit .

Secondary outcomes

- The impact each of the eight red flags has on recruitment predictions.

RESEARCH METHODS

The dedicated trial managers who handle local site set-up are deeply involved in this process and will (we speculate) have a good sense of whether a site will go on to recruit to its target. ESP2 asks trial managers to use our guided prediction form to predict site recruitment, which we will then compare to actual recruitment performance. If the form helps prediction, it could be rolled out as a trial management tool to enable time and energy to be directed to sites with a good chance of recruitment success, and prevent it being wasted on sites that are highly unlikely to meet their targets. It could also be a useful tool to help less experienced trial managers.

STUDY DESIGN

Inclusion criteria

- The people providing predictions must be trial managers responsible for setting up trial recruitment sites and carrying out site initiation training with site staff. Some people undertaking this activity may have a different job title; they will be eligible to take part on the basis of undertaking this activity.
- The recruitment prediction is for a site in a randomised or non-randomised trial. The site and the individual making the prediction can be anywhere in the world.
- The trial must be testing one or more interventions.
- The trial must be opening new recruitment sites.
- Individuals should be willing to make at least one prediction. These predictions can be for different sites within the same trial, sites across many trials, or a combination of both. There is no limit to the number of predictions a trial manager can make.

Exclusion criterion

- Cluster randomised trials.

Proposed start date and end date

Start: Autumn 2019.

End: Once we have around 1000 predictions. We expect that this may take up to two years, plus a further six months to allow the sites involved in the last predictions to do some recruitment.

Recruitment

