We are interested in the ability of trial managers to correctly identify a site that will fail to recruit. For a diagnostic test this is called specificity, the proportion of correct negatives. Our pilot work found a specificity of 32% (Bruhn et al 2019). We expect the eight red flags to improve this substantially because they were identified through qualitative work in our pilot as markers of poor recruitment.

The sample size is dependent on assumptions about prevalence (the proportion of sites that fail to recruit), sensitivity and specificity. The specificity of 32% seen in the pilot *without* the use of the red flags is too low for trial management decision-making. Instead we believe a 75% specificity is what we should target– it is high enough that the prediction cannot be ignored – and we want to be certain that the 95% confidence interval around a result of 75% has a lower bound above 65% (i.e. we want some certainty that our specificity is not actually much lower than 75%).

Our pilot (Bruhn et al 2019) had a recruitment failure prevalence of 40% of sites. The sensitivity in the pilot was 82%.

Therefore, if we take a recruitment failure rate of 40%, a sensitivity of 90% (a bit higher than the pilot because we expect the red flags to help here too) and the measured specificity of 75% that we want, a sample size of 1000 predictions would give us 80% power to rule out specificity of below 70%. Halving the sample size to 500 and with 40% prevalence, 90% sensitivity and a measured specificity of 73%, we'll still have adequate power to rule out a lower bound to of 65%.

Therefore, we will aim for 1000 predictions. However we would still have acceptable power, based on reasonable assumptions, providing we reach 500 predictions. In our pilot we got 56 predictions from one trials unit, ten trial managers and eight trials. In the UK as a whole there are 51 registered trials units and well over 1200 trial managers. Each trials unit is likely to have a portfolio of at least ten trials. Clearly, our web-based study is open to trial managers well beyond the UK. The pool of potential predictions is therefore very large. A target of 1000 predictions is not at all implausible.

ANALYSIS

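### The 80% power stated for excluding a specificity of 70% with 1000 predictions is about 57–64%, because specificity is estimated only in the roughly 400 sites that fail

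*Protocol*

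**What the plan says.** Under Outcome measures the Protocol states: "The primary outcome is the proportion of correct predictions made by trial managers of sites that fail to recruit". The Sample size section repeats the aim ("We are interested in the ability of trial managers to correctly identify a site that will fail to recruit"), calls this quantity specificity, and defines prevalence as "the proportion of sites that fail to recruit".

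The section then makes three quantitative statements:

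- **Precision aim.** The 95% confidence interval around a result of 75% should be one that "has a lower bound above 65" per cent.
- **Main target.** "if we take a recruitment failure rate of 40%, a sensitivity of 90" per cent, and the measured specificity is 75%, then "a sample size of 1000 predictions would give us 80% power to rule out specificity of below 70" per cent.
- **Fallback.** "Halving the sample size to 500 and with 40% prevalence, 90% sensitivity and a measured specificity of 73" per cent, power to exclude 65% is called adequate. No power figure is given.

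The section gives no alpha level or test for the power statement; the only level in it is the 95% confidence interval. The End of the study section uses 500 predictions as the threshold for stopping new predictions at two years.

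**The concern.** The Protocol's definitions put specificity on failing sites only. With 40% failing, 1000 predictions give about 400 observations for the primary outcome, and the other 600 or so say nothing about specificity. A five-point difference, 75% against 70%, is small for 400 binary observations, so 80% power looked too high.

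This is the only power figure given for the primary outcome, and it supports the target of 1000. If observed specificity came out near 75% with an interval that included 70%, a reader relying on the Protocol would think the study had an 80% chance of excluding 70% when its chance was nearer 60%.

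**Working it through.** **Inputs** (Protocol, Sample size): failure rate 40%; specificity 75% against 70% for 1000 predictions, and 73% against 65% for 500; 95% confidence interval, read as two-sided 5%. The assumed sensitivity of 90% concerns succeeding sites and does not affect power for specificity.

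**Denominator.** 0.40 × 1000 = 400 failing sites; 0.40 × 500 = 200. The pilot figures under Background confirm the definition. Of 56 sites, 22 failing with 7 correctly predicted and 34 succeeding with 28 correctly predicted give specificity 7/22 = 32%, sensitivity 28/34 = 82%, and correct predictions of 28/43 = 65% and 7/13 = 54%. All four match the text, so specificity there is taken over failing sites.

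**Formulas**, with p0 the value to exclude, p1 the true value and n the number of failing sites:

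- Wald: power = Φ[(p1 − p0)/√(p1(1 − p1)/n) − z]
- Score: power = Φ[(p1 − p0 − z√(p0(1 − p0)/n))/√(p1(1 − p1)/n)]
- Exact: binomial probability under p1 of reaching the exact critical count under p0

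**Stated claim, n = 400, z = 1.96.**

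- Wald: √(0.75 × 0.25/400) = 0.02165; 0.05/0.02165 − 1.96 = 0.349; Φ = 63.7%.
- Score: critical value 0.70 + 1.96 × √(0.70 × 0.30/400) = 0.7449; (0.75 − 0.7449)/0.02165 = 0.235; Φ = 59.3%.
- Exact: at least 299 of 400 are needed; power 57.2%.

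**Looking for the stated 80%.** With n = 600, the 60% of sites that succeed, Wald gives 0.05/√(0.75 × 0.25/600) − 1.96 = 0.868; Φ = 80.7%. With all 1000 as denominator the three methods give 94–96%. With n = 400, only a one-sided 10% level reaches 80% (81–85%), and the Protocol mentions no such level.

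| Setting | Exact | Score | Wald |
|---|---|---|---|
| n = 400, 75% v 70%, two-sided 5% | 57.2% | 59.3% | 63.7% |
| n = 400, 75% v 70%, one-sided 5% | 70.1% | 71.5% | 74.7% |
| n = 600, 75% v 70%, two-sided 5% | 76.1% | 77.5% | 80.7% |
| n = 200, 73% v 65%, two-sided 5% | 65.8% | 67.1% | 72.2% |
| n = 200, 73% v 65%, one-sided 5% | 76.5% | 78.3% | 81.7% |
| n = 400, 75% v 65%, two-sided 5% | 99.0% | 99.3% | 99.6% |
| n = 200, 75% v 65%, two-sided 5% | 85.5% | 86.6% | 90.4% |

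Treating the number of failing sites as random (binomial, 40% of 1000) gives 58.3% by the exact rule.

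**Number needed for 80% power, 75% v 70%, two-sided 5%.** Score: 638 failing sites, and 638/0.40 = 1595 predictions. Wald: 589 failing sites, about 1472 predictions.

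**Precision aim.** The Wald lower 95% limit at an observed 75% is 0.75 − 1.96 × 0.02165 = 70.8% with 400 failing sites and 69.0% with 200. At an observed 73% of 200 it is 66.8%. All exceed 65%.

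**The case against.** The strongest reply is that the aim actually stated is the precision aim, and it is met at both sizes. That stands. It means the study is large enough for that aim, but it does not make the 80% figure follow from its inputs.

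A second reply is that no alpha is stated, so a single recomputed value claims too much. That also stands, which is why a range is given here. No method tried at a 5% level, one-sided or two-sided, reaches 80% with 400 sites.

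A third is that the Protocol speaks of a measured specificity. An observed 75% in 400 sites does exclude 70% (lower limit 70.8%). Power, however, is a probability computed at an assumed true value, and at a true 75% it is not 80%.

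Some stronger readings are tempting but not supported:

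- **That the fallback's power is also misstated.** It is only called adequate, so there is no figure to contradict, and about 77–82% at one-sided 5% could fairly be described that way.
- **That the study is weaker than stated at either size, which would undermine the stopping threshold of 500.** The shortfall is shown only for the 70% bound at 1000 predictions. Against 65% at a true 75%, power is about 99% with 400 failing sites and about 86–90% with 200.
- **That success is undefined because the bound moves between 65% and 70%.** The different bounds can be read as planning scenarios, and excluding 70% also excludes 65%. Choosing one bound is partly preference.

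**Conclusion.** The point holds for the 1000-prediction power statement. On the Protocol's own definitions and inputs, power to exclude 70% at a true specificity of 75% is about 57–64% at two-sided 5% and 70–75% at one-sided 5%, not 80%. The fallback contradicts no number, but calling its power adequate leaves about 66–72% (two-sided) or 77–82% (one-sided) unstated.

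A reader might infer from the match at n = 600 that the two classes of site were swapped. That is plausible, but the Protocol does not show how the 80% was obtained, and the finding does not rely on it.

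The figures assume exactly 40% failing (except in the random-number check), independent predictions and a known outcome for every site. Positive clustering by trial manager or trial, or missing recruitment updates, would lower power further. The two-sided 5% level is inferred from the 95% interval.

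**What to change.** Restate the power in the Sample size section, for example:

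- 1000 predictions (about 400 failing sites) give about 60% power to exclude a specificity of 70%, and about 99% to exclude 65%, if true specificity is 75%.
- 500 predictions (about 200 failing sites) give about 86–90% power to exclude 65% at a true 75%, and about 66–72% at a true 73%.

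These are two-sided 5% figures. The text should state the alpha level and the method, replace each range with that method's value, and say that power depends on the number of failing sites with a known outcome. The precision aim can stay as the stated target.

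The cost is Protocol wording only. The claim against 70% becomes less favourable, and no extra predictions are needed unless 80% power against 70% is itself required, which would take roughly 1472 to 1595.

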Trial managers will then be asked to fill in a short, online questionnaire for each site they carry out site initiation training for, and give a prediction as to whether that site is likely to meet its recruitment target. Trial managers will also be asked to pick the three red flags on our prediction questionnaire that were most important for their prediction. Trial managers may not wish to make predictions for all sites; they are not required to do so. However, there is no limit to the number of predictions a trial manager can make (although they should not make multiple predictions for the same recruitment site for the same trial).

Follow-up

Trial managers will be asked to tell us the total recruitment at each site for which they made a prediction 6 months after their prediction and again at 12 months after the prediction. This request will be sent automatically to trial managers via the study website.

This will give us actual site recruitment, which we can then compare to the target recruitment that the trial manager gave when making his or her prediction. For example, a trial manager may say that the recruitment target for a site is 80 participants at 12-months. She predicts recruitment failure at this site. At 6 months the trial manager tells us actual recruitment is 34 and at 12-months actual recruitment is 67. Her prediction of recruitment failure was correct.

At each timepoint we will also include an update option in case the site has been closed or the recruitment timeline amended.

Withdrawal

Trial managers are free to withdraw from taking part in ESP2 at any point during the study. Trial managers are encouraged to complete a prediction form for every site they complete site initiation training for but are able to participate to whatever extent they wish – for example, they may complete prediction forms for some but not all sites that they carry out site initiation training for.

If a trial manager withdraws because he or she is moving to a new post, we will encourage the replacement trial manager to register if he or she wishes to, in order to provide predictions and/or recruitment updates. This will help to reduce missing data.

Sample size

Our sample size decisions have been guided by [name], statistician and Director of CHaRT.

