The website has been developed by data management staff at CHaRT and complies with GDPR. Staff taking part in the study will be assured that all predictions will be kept confidential. It will not be possible to identify individual recruitment sites or trials in reports from the study. Data will be kept for 3 years after publication and will be available from the project team on reasonable request and taking care to avoid identifying trials and trial managers.

STUDY MANAGEMENT

The study will be managed by the investigators listed above. Participating trial managers will be able to contact any of the investigators for information about the study, or if they have queries via an ESP2 mailbox.

END OF THE STUDY

The study will run until we have 1000 predictions, which we expect to take no more than two years. If at two years, we have more than 500 predictions but fewer than 1000, we will stop the study for new predictions. An additional six months beyond this point will allow some recruitment at sites involved in predictions made at the end of the prediction period. Analysis will occur after this time.

AUTHORSHIP AND PUBLICATION

We will follow International Committee of Medical Journal Editors (ICMJE) guidelines on authorship (see <http://www.icmje.org/recommendations/browse/roles-and-responsibilities/defining-the-role-of-authors-and-contributors.html>).

This work will be disseminated at meetings and conferences such as the UK Trial Managers' Network Annual Meeting, Society of Clinical Trials Conference and the International Clinical Trials Methodology Conference. The results will also be published in a peer reviewed journal. In any publication resulting from this work, it will not be possible to identify individual trial managers, trials or sites. Trial managers who contribute predictions and recruitment data to the ESP2 study will be appropriately acknowledged. A summary of results will be sent to all participating trial managers by email.

REFERENCES

Peter Bower, Valerie Brueton, Carrol Gamble, Shaun Treweek, Catrin Tudur Smith, Bridget Young, Paula Williamson (2014) Interventions to improve recruitment and retention in clinical trials: a survey and workshop to assess current practice and future priorities. *Trials* 15:399.

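### The power stated at 1000 and 500 counts predictions made, with no allowance for predictions whose site outcome is never reported

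*Protocol*

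**What the plan says.** The Outcome measures section defines the primary outcome as "the proportion of correct predictions made by trial managers of sites that fail to recruit". The Sample size section calls this specificity and takes a failure prevalence of 40%.

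That section states that "a sample size of 1000 predictions would give us 80% power to rule out specificity of below 70" per cent, at a specificity of 75%. For half that number it assumes a specificity of 73% and a value of 65% to be ruled out. It calls the power adequate without giving a figure, and adds that "we would still have acceptable power, based on reasonable assumptions, providing we reach 500 predictions".

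The closing rule counts the same unit. Under End of the study: "The study will run until we have 1000 predictions, which we expect to take no more than two years", and then "If at two years, we have more than 500 predictions but fewer than 1000, we will stop the study for new predictions". A further six months follow so that sites can recruit. The Proposed start date and end date section also ends the study on about 1000 predictions.

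The outcome comes later and from the manager. The Follow-up section puts it this way: "Trial managers will be asked to tell us the total recruitment at each site for which they made a prediction 6 months after their prediction", with a second request at 12 months. Under Withdrawal, managers may leave at any point. When one changes post, the successor is encouraged to register, and the protocol says of this: "This will help to reduce missing data".

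**The concern.** A prediction adds to specificity only once the site's actual recruitment is known and the site is found to have failed. The sample size and the closing rule count an earlier event, the entry of the prediction. The protocol expects some outcomes to be missing, since it describes a measure that reduces the loss and does not claim to remove it. Neither the 1000 nor the 500 is inflated, and no loss rate is given.

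The power is therefore stated for a number that the plan does not expect to analyse. The shortfall arises even if outcomes are missing completely at random. It matters most at 500, which has no reserve beneath it: a study closed at 510 predictions with 10% lost has 510 x 0.90 = 459 scored.

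**Working it through.** **Inputs from the protocol.** Failure prevalence is 40%. At 1000 predictions, specificity is 75% against 70%, with stated power 80%. At 500 predictions, it is 73% against 65%, with no power figure. The level is not stated for the power; the protocol's use of a 95% interval implies two-sided 5%.

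**Assumed.** Loss d of 10% and 20%, because the protocol gives none.

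**Formulas**, with n the number of sites in the specificity denominator:

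- Scored sites: n = N x share x (1 - d).
- Wald power: Phi[(p1 - p0)/sqrt(p1(1 - p1)/n) - 1.96].
- Score power: Phi[(p1 - p0 - 1.96 sqrt(p0(1 - p0)/n))/sqrt(p1(1 - p1)/n)].

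**Step 1: the printed 80%.** The denominator defined by the primary outcome is failing sites, 0.40 x 1000 = 400. With no loss, two-sided power is then 59.3% (score), 63.7% (Wald) or 57.2% (exact). One-sided it is 71.5%, 74.7% or 70.1%. None is close to 80%. With 0.60 x 1000 = 600 sites and the two-sided Wald form, sqrt(0.1875/600) = 0.01768, 0.05/0.01768 = 2.828, and Phi(2.828 - 1.96) = 80.7%. This is the only variant tried that comes within 2 points. It uses all 1000 predictions, so it contains no attrition either.

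**Step 2: the effect of loss, on both bases.**

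| Predictions made | Basis | No loss | 10% loss | 20% loss |
|---|---|---|---|---|
| 1000 (75% v 70%) | 60% of sites, Wald | 80.7% (n = 600) | 76.5% (540) | 71.6% (480) |
| 500 (73% v 65%) | 60% of sites, Wald | 87.7% (300) | 84.2% (270) | 79.7% (240) |
| 1000 (75% v 70%) | failing sites, score | 59.3% (400) | 54.6% (360) | 49.7% (320) |
| 500 (73% v 65%) | failing sites, score | 67.1% (200) | 62.2% (180) | 56.9% (160) |

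Each 10% lost costs between 3.5 points (87.7 to 84.2) and 5.3 points (62.2 to 56.9), so roughly 4 to 5. Comparing rows at 1000 with no loss, the drop from 80.7% to 59.3% comes mainly from the denominator and partly from the choice of test (Wald on 400 sites gives 63.7%). None of it is attrition.

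**Step 3: the precision aim.** The Sample size section also wants the 95% interval around an observed 75% to have a lower limit above 65%. With 500 made and 50% lost, failing sites number 500 x 0.40 x 0.50 = 100. The lower limit is 0.75 - 1.96 x sqrt(0.1875/100) = 0.75 - 0.085 = 66.5% (Wald), or 65.7% (Wilson). The aim is still met.

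**Step 4: predictions needed to offset loss.** With N/(1 - d), 1000 scored need 1112 made at 10% loss and 1250 at 20%. For 500 scored, the figures are 556 and 625.

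**The case against.** The best defence is that the effect is modest and its size unknown. No loss rate is given. The requests are automatic, there are two of them, and a successor may supply the update. The pro rata rule under Analysis might let a 6-month report score a prediction whose 12-month report is missing, so one missed reply need not lose it. This stands, and it is why only a range can be shown. It does not make zero loss the protocol's expectation.

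The handling of missing outcomes may also lie in an analysis plan not shown here. That is fair, but the sample size, the floor and the closing rule are fixed in this protocol.

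The gap between 1000 and 500 might be offered as the allowance. Both figures count predictions made, and 500 is presented as a smaller study with its own assumptions, not as 1000 after loss.

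A reader might infer that a study closed just above 500 fails the protocol's own adequacy criterion. The documents do not support that. They set no numerical power at 500, and on the basis that reproduces the printed 80%, the floor still has 79.7% after 20% loss. A reader might also blame attrition for the whole fall from 80% to 59%. That gap is present with no loss at all.

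**Conclusion.** The point holds in a limited form. The 1000 and 500 are counts of predictions made, only predictions with a reported outcome can be scored, and the stated power makes no allowance for the difference. At an assumed 10% to 20% loss, power at 1000 falls to 76.5% and 71.6% on the protocol's apparent basis, or to 54.6% and 49.7% on the failing-site basis. The damage is confined to the two power statements, since the precision aim withstands even 50% loss at 500 predictions. The calculation treats predictions as independent and losses as unrelated to outcome; it makes no claim that the loss is biased. The change is worth making because it is cheap, but it is secondary to the denominator error, which is far larger.

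**What to change.** - **Sample size:** state power for predictions with a reported outcome, at an explicit assumed loss (for example 10% and 20%). Make the statement of acceptable power at 500 refer to predictions with a reported outcome.
- **Proposed start date and end date, and End of the study:** keep closing entry on predictions made and at the two-year limit. Outcomes arrive 6 to 12 months after entry, so a count of reported outcomes cannot close entry in real time. Judge the 1000 target and the 500 floor on expected scored predictions: predictions made multiplied by the response rate seen so far at the 6- and 12-month requests.
- **Reporting:** if fewer than 500 are scored, report the precision achieved and do not claim the stated power.

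The cost is wording and one recalculation, and the stated power becomes less favourable. No extension beyond two years is required. Offsetting the loss within that limit is optional and not trivial: reaching 1000 scored needs 112 extra predictions at 10% loss or 250 at 20%, each with two follow-up requests.
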